#### 4.5.1.1 Adverse Events of Special Interest and Possible Interest

Preferred terms used to identify adverse events of special interest and possible interest (as defined in 3.2.3) will be listed before DBL and documented in the Study Master File. Grouped summary tables of certain MedDRA preferred terms will be produced and may also show the individual preferred terms which constitute each AESI/AEPI grouping. Groupings will be based on preferred terms provided by the medical team prior to DBL, and a listing of the preferred terms in each grouping will be provided.

Summaries of the above-mentioned grouped AE categories will include number (%) of patients who have:

- Any AESI/AEPI
- Any AESI/AEPI by SOC, PT and maximum CTCAE grade
- Any AESI/AEPI of maximum CTCAE grade 3 or 4
- Any serious AESI/AEPI
- Any AESI/AEPI with outcome of death
- Any AESI/AEPI possibly related to study treatment
- Any AESI/AEPI leading to concomitant medication use (steroids)
- Any AESI/AEPI leading to concomitant medication use (high dose steroids)
- Any AESI/AEPI leading to concomitant medication use (endocrine therapy)
- Any AESI/AEPI leading to concomitant medication use (other immunosuppressants)
- At least one AESI/AEPI leading to discontinuation of study treatment
- Possibly related AESI/AEPI leading to discontinuation of study treatment
- Time to onset of first AESI/AEPI (days)
- Duration (days) of AESI/AEPI

An overall AESI/AEPI summary will be presented, including number and percentage of patients in each of these categories. Any AESI/AEPI presented by outcome will also be provided.

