8.3.3 Follow-up of AEs and SAEs

After the initial AE/SAE report, the Investigator is required to proactively follow each patient at subsequent visits/contacts. All AEs, SAEs, and AESIs (as defined in Section [8.3.12](#)) will be followed until resolution, stabilization, the event is otherwise explained, or the patient is lost to follow-up.

Any AEs that are unresolved at the patient's last AE assessment in the study are followed up by the Investigator for as long as medically indicated (this may be beyond the 90 days after the last dose of durvalumab), but without further recording in the CRF. AstraZeneca retains the right to request additional information for any patient with ongoing AE(s)/SAE(s) at the end of the study, if judged necessary.

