9.4 Outcome measures for analyses

- 1 **AE:** Number and proportion of patients with AEs in total and by causality and severity
- 2 **AE:** Number and proportion of patients with Grade 3 and Grade 4 AEs in total and by causality
- 3 **SAE:** Number and proportion of patients with SAEs in total and by causality and severity
- 4 **AEs leading to death:** Number and proportion of patients with AEs leading to death
- 5 **AEs leading to treatment interruption or discontinuation:** Number and proportion of patients with AEs leading to treatment interruption and/or discontinuation
- 6 **AESI:** Defined as an AE of scientific and medical interest specific to understanding of the IP. AESIs for durvalumab include, but are not limited to, events with a potential inflammatory or immune-mediated mechanism and which may require more frequent monitoring and/or interventions such as steroids, immunosuppressants, and/or hormone replacement therapy. In order to further characterize safety objectives related to AESIs, outcome measures will be assessed, which may include (and are not necessarily limited to) the following:
 - (a) Number and proportion of patients with AESIs, by predefined type (or newly defined by this study) in total and by seriousness, severity and causality, including immune-relatedness;

- (b) Number and proportion of patients who received steroids, immunosuppressants, and/or hormone replacement therapy to manage AESIs;
- (c) Time from start of durvalumab to the onset of an AESI predefined type, all interventions of AESIs by type of intervention (including intervention with steroids, immunosuppressants, and/or hormone replacement therapy), and time from onset of an AESI type to resolution;
- (d) Duration of the intervention with steroids, immunosuppressants, and/or hormone replacement therapy until the resolution of AESI;
- (e) The imAEs will be assessed as a subset of AESIs. An imAE is defined as an AESI that is associated with drug exposure and is consistent with an immune-mediated MOA and where there is no clear alternate etiology.
- (f) Laboratory findings, vital signs, and other safety parameters associated with AESIs will be summarized as part of the AESI outcome measures.

7 **PFS:** Defined as the time from the first date of treatment until the date of objective disease progression or death (by any cause in the absence of progression) regardless of whether the patient withdraws from IP or receives another anticancer therapy prior to progression.

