## 4. ANALYSIS METHODS

### 4.1 General Principles

#### 4.1.1 General Statistical Considerations

The following general statistical considerations will be applied for the analyses and presentation of the data. In case of any specific deviations, methods will be specifically noted on the relevant output.

- All data, demography, baseline characteristics, safety, efficacy and biomarkers, will be summarized using descriptive statistics, as appropriate for the type of data, for the SAF. In addition, all efficacy and safety data and some selected relevant data (eg, patient disposition, demography and baseline characteristics) will be summarised separately for each cohort (standard radiotherapy and palliative radiotherapy) and overall.
- Continuous variables will be summarized by the number of observations (n), mean, standard deviation, median, minimum, and maximum.
- For the continuous data, the summary statistics will be displayed with the following accuracy (number of dps):
  - The minimum and maximum with same accuracy as the raw data.
  - The mean and median will be rounded to 1 additional dp more than the number of dps in the raw data.
  - The standard deviation will be rounded to 2 additional dps more than the number of dps in the raw data.
  - If the number of observations is 1, the SD will not be derived.
- Categorical variables will be summarized by frequency counts and percentages for each category and percentages will be rounded to one dp.
- As a default, percentages will be calculated using the number of patients who have non-missing data as the denominator. Therefore, percentages for missing data will not be presented in the results. If the denominator is different from this default, it will be explained in a footnote to the output.
- SAS® version 9.4 or higher will be used for all analyses.
- Exact CIs for proportions will be calculated using the Clopper-Pearson method.

- For percentiles of survival times based on the Kaplan-Meier method (eg, median survival), CIs will be calculated using the default method available in the SAS LIFETEST procedure (ie, the Klein and Moeschberger extension of the Brookmeyer-Crowley method).
- For point-estimates of survival based on the Kaplan-Meier method (eg, for PFS12), CIs will be calculated using the default method available in the SAS LIFETEST procedure (ie, using Greenwood's estimate of standard error and a log-log transformation).

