#### **4.1.3 Handling of Missing Data**

Missing safety data will generally not be imputed. However, safety assessment values of the form of “<x” (ie, below the lower limit of quantification) or >x (ie, above the upper limit of quantification) will be imputed as “x” in the calculation of summary statistics but displayed as “<x” or “>x” in the listings.

If the start date of the concomitant medication or AE is missing, the following rules will be applied:

- If the year is missing, the year should be imputed as the year that patient received the first dose of durvalumab.
- If the year is available and the month and day are missing, then impute the month as January and the day as 01 unless year is the same as first dose date then impute first dose date.
- If the year and month are available and the day is missing, impute the day as 01 (the first day of the month) unless month is same as month of first dose of study drug then impute first dose date.

- If the start date is completely missing and end date is present, then take day and month as 01Jan and the year from end date.

If the stop date of the concomitant medication or AE is missing, the following rules will be applied:

- If the year is missing, the year should be imputed as the year that patient received the last dose of durvalumab.
- If the year is available and the month and day are missing, then impute the month as December and the day as 31 unless year is the same as last dose date then impute last dose date. If the last dose date is not available then DCO date will be used.
- If the year and month are available and the day is missing, impute the day as the last day of the month (eg, 28, 29, 30 or 31) unless month is same as month of last dose date then impute last dose date. If the last dose date is not available, DCO date will be used.
- If the end date is completely missing, then look at whether the AE/medication is still ongoing before imputing a date and also when it started in relation to study drug. If the ongoing flag is missing then assume that AE is still present / medication is still being taken (i.e. do not impute a date). If the AE/medication has stopped and start date is prior to first dose date then impute the 1st dose date, if it started on or after first dose date then impute a date that is 1 day after the last dose date.

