#### **4.5.1.2 Immune-mediated Adverse events (imAEs)**

The imAEs will be summarized in the similar manner as for the summaries for AESI/AEPI described above.

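### AESI, AEPI and imAE duration has no definition and no rule for unresolved events; under the SAP defaults only resolved events contribute, so the summary is biased downward by an unknown amount

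*SAP*

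**What the plan says.** SAP 4.5.1.1 gives a list of AESI/AEPI summaries introduced as numbers and percentages of patients. One item is "Duration (days) of AESI/AEPI". No start or end rule, unit of analysis or statistic is attached to it. SAP 4.5.1.2 adds: "The imAEs will be summarized in the similar manner as for the summaries for AESI/AEPI described above".

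The rules that apply by default are these.

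- SAP 4.1.1: "Continuous variables will be summarized by the number of observations (n), mean, standard deviation, median, minimum, and maximum".
- SAP 4.1.3: "Missing safety data will generally not be imputed". For a wholly missing end date, the programmer must "look at whether the AE/medication is still ongoing before imputing a date". If the ongoing flag is itself missing, the instruction is to "assume that AE is still present / medication is still being taken (i.e. do not impute a date"). A date is imputed only for an event known to have stopped.
- Protocol 8.3.3: events unresolved at the patient's last AE assessment are followed clinically "but without further recording in the CRF".

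Protocol 9.4, item 6(c), describes the related measure as "time from onset of an AESI type to resolution", in a list of measures that the AESI assessment may include. SAP 4.5.1.1 also plans a presentation of AESI/AEPI by outcome.

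**The concern.** Time from onset to resolution is censored for every event still open when recording ends. A mean or median taken over completed durations answers how long an event lasted given that it resolved in time, but it will be read as how long the toxicity lasts. The events left out are disproportionately the long ones.

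Open events are to be expected. AE collection ends 90 days after the last dose (Protocol 8.3.2). The primary analysis cut-off is expected 6 months after the last patient's first dose (SAP 5), while treatment can run for 12 months. Safety is the main aim of the study, AESIs and imAEs are named secondary safety endpoints, and Protocol 9.5 says the data from this analysis would be published to support real-world use.

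**Working it through.** **Step 1. What the rules produce.** The plan gives no figure for AE duration, so there is nothing to reproduce. An event with onset and stop dates has a duration. An ongoing event has no stop date, none is imputed, and no later one reaches the CRF. SAP 4.1.2 imputes only partial dates when deriving time to resolution. SAP 2.1.1 refers to defined censoring for time-to-event endpoints, but none is defined for AE duration. SAP 4.4.4, by contrast, uses Kaplan-Meier for duration of response. Applied literally, n, mean and median are computed over resolved events only.

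**Step 2. Direction.** Let T be the true duration and C the time from onset to the end of recording, assumed independent of T. An event is kept if T ≤ C. The chance of being kept falls as T grows, so the kept durations are stochastically shorter than all durations. The direction needs no assumption about how long events last.

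**Step 3. Size when some events never resolve.** Assumptions, none from the documents: resolving events are exponential with median 30 days, a fraction p never resolves, and recording continues for 60 to 365 days (uniform) after onset. The median t over all events solves

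p + (1 − p)·2^(−t/30) = 0.5, so t = −30·log2[(0.5 − p)/(1 − p)].

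For example, p = 0.20 gives −30·log2(0.3/0.8) = 42.4 days. The resolved-only median does not depend on p, because never-resolving events are dropped whatever their number. Simulation puts it between 28 and 29 days throughout.

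| p never resolving | Median, all events (days) | Resolved-only median (days) |
|---|---|---|
| 0% | 30.0 | about 28 |
| 5% | 32.3 | about 28 |
| 10% | 35.1 | about 28 |
| 20% | 42.4 | about 28 |
| 40% | 77.5 | about 28 |

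**Step 4. Size when every event eventually resolves.** For true median m and a fixed window C, the resolved fraction is F = 1 − 2^(−C/m) and the resolved-only median is −m·log2(1 − F/2).

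- m = 30, C = 180: F = 0.984, resolved-only median 29.3 days. The bias is negligible.
- m = 60, C = 90: F = 0.646, resolved-only median 33.8 days; 35.4% of events dropped.
- m = 120, C = 180: F = 0.646, resolved-only median 67.6 days; 35.4% dropped.

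**Step 5. Does a censored analysis recover it?** A simulation of 200,000 events took onset on days 1–183 and closed recording 90 days after a last dose at a random cycle. With all events resolving and a true median of 60 days, Kaplan-Meier gave 60 days and resolved-only 43. With 20% never resolving (overall median about 84 days), Kaplan-Meier gave 84 days and resolved-only 43.

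**Step 6. Would it work at this study's size?** SAP 3.2.3.2 names 19 categories and about 102 patients are treated. If the PACIFIC rates in Protocol 2.3.2.1 held, there would be about 0.339 × 102 = 35 patients with pneumonitis or radiation pneumonitis and 0.116 × 102 = 12 with hypothyroidism. In the Step 3 model with 30% to 40% never resolving, the upper 95% limit for the Kaplan-Meier median is not reached in roughly 70% to 90% of samples of 12 and 32% to 77% of samples of 35. The method is useful for the pooled set and the larger categories, not for all 19.

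**The case against.** The strongest reply is that nobody chose a biased analysis. A reader might infer that the SAP instructs unresolved events to be excluded. It does not. The duration item names no statistic, SAP 4.1.1 asks for statistics suited to the type of data and allows deviations to be noted on the output, and leaving an ongoing event without an end date is also what a censored analysis needs. That stands as a limit on the wording: exclusion follows from defaults and silence. It does not remove the problem, because nothing in the plan leads a programmer to another result.

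A reader might also infer that the protocol fixes time to resolution as a time-to-event endpoint. It is one of several measures that the AESI assessment may include. Nor does the protocol call endocrinopathies or pneumonitis persistent; it lists them as AESIs.

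Mitigations exist. The outcome presentation may show how many events are unresolved, the listings give resolution dates for resolved events, and a printed n would reveal a shortfall. These help a careful reader, but the printed median stays too short. The sponsor may request more information on events ongoing at study end, but no rule brings it into this summary. The recording cut-off limits a Kaplan-Meier analysis too, but that analysis uses the partial follow-up instead of discarding it.

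The objection to blanket Kaplan-Meier medians also stands: most categories will be sparse, and censoring at death treats a patient who can no longer recover as if resolution were still possible. The fix below allows for both.

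**Conclusion.** The point holds as a gap with a predictable consequence. Followed as written, the plan gives a duration only for resolved AESIs, AEPIs and imAEs, and that summary is biased downward. The direction rests on recording time being unrelated to how long an event lasts.

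The size cannot be taken from the documents, which give neither durations nor a never-resolving share. With an assumed 30-day median for resolving events, the gap runs from about 28 against 30 days when all resolve to about 28 against 78 days when 40% never do. A reader might take the upper end as the expected error; nothing in the documents supports that, and for short-lived events the bias is slight.

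Nor does the point reach the main result. This is a descriptive secondary safety summary, and the incidence of Grade 3 and 4 possibly related events does not use duration. The change should be made, but it is not critical to the trial's conclusions.

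**What to change.** Amend SAP 4.5.1.1, and 4.5.1.2 by reference, as follows.

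- Define duration as onset to resolution and state whether the unit is the event or the patient.
- For all AESIs combined, all imAEs combined, and each category reaching a minimum event count set in advance, report Kaplan-Meier time to resolution. Censor events still ongoing at the earlier of the last AE assessment and the data cut-off.
- Show deaths with the event unresolved separately, or treat death as a competing event.
- For sparser categories, keep the simple summary, label it as resolved events only, and print the number unresolved beside it.

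The cost is SAP wording and one extra table. Onset, stop date and outcome are already collected (Protocol 8.3.4), and Kaplan-Meier is already programmed for duration of response. The downside is that some medians or upper confidence limits will not be reached and must be reported as such.

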#### **4.5.1.2 Immune-mediated Adverse events (imAEs)**

The imAEs will be summarized in the similar manner as for the summaries for AESI/AEPI described above.

#### **4.5.1.3 COVID-19 related Adverse events**

The following summaries of AE data will be presented including the number and percentage of patients with:

- Any AE in patients with confirmed/suspected COVID-19 infection
- Any AE in patients without confirmed/suspected COVID-19 infection
- Any AE by SOC, PT and maximum CTCAE grade in patients with confirmed/suspected COVID-19 infection.
- Any AE by SOC, PT and maximum CTCAE grade in patients without confirmed/suspected COVID-19 infection
- Any AE associated with COVID-19 infection by SOC and PT
- Any AE excluding AEs associated with COVID-19 infection by SOC and PT
- Any AE with confirmed/suspected COVID-19 infection by SOC and PT
- Any AE excluding confirmed COVID-19 infection by SOC and PT
- Any AE associated with COVID-19 infection and with outcome of death by SOC and PT
- Any AE excluding associated with COVID-19 infection and with outcome of death by SOC and PT
- Any AE associated with COVID-19 infection leading to discontinuation of investigational product by SOC and PT
- Any AE excluding associated with COVID-19 infection leading to discontinuation of investigational product by SOC and PT

#### **4.5.2 Electrocardiograms**

The data for the ECG are used for safety monitoring and to identify AEs. No summaries or listings will be created.

